10.4.4 Safety Analyses

Patients will be monitored for the occurrence of possible adverse events using a standardized data collection form prior to hospital discharge. All serious events which many potentially be adverse reactions (anaphylaxis, serious rash or death) will be assessed by the primary investigator. The study team and the NYU SOM Institutional Review Board will be notified within one day of identification of the event by study personnel.

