5.7.2 Handling of Participant Withdrawals or Termination

For patients who have withdrawn or terminated from the study, follow up telephone calls will be conducted to assess for side effects. One phone call two weeks after the patient has been declared

CONFIDENTIAL

This material is the property of the NYU School of Medicine and Langone Medical Center. Do not disclose or use except as authorized in writing by the study sponsor
Interventional Template Version: 28 APR 2017

withdrawn or terminated will be conducted. For patients who remain in the study, but discontinue the study agent, they will be asked to complete the follow up questionnaire when they present for study visits to assess for adverse reactions or side effects. Adverse events from the drug are local at the site of application and should subside with the discontinuation of the product. Therefore, long term follow up for adverse events is deemed unnecessary.

A participant will be stated as lost to follow-up (and therefore withdrawn/terminated) if: they have missed all three study visits, the study team has attempted weekly phone calls to parent/guardian for three weeks without answer or success of having the participant return for study visit.

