6.1.9 Duration of Therapy

Each ointment will be applied for five consecutive days. The five days is necessary for an 'evaluable' participant

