6.2 Study Agent Accountability Procedures

The study agents will be allocated and dispensed by the NYULMC Investigational Research Pharmacy. The pharmacy and research pharmacist will receive shipment of the agents, allocated into individual unidentifiable container and be responsible for the blinding of the agents. The dispensed drugs will be given to the PI or co-investigator in blinded fashion by the Investigational Pharmacy for enrolled patients at the time of enrollment visit. The PI/co-investigator will distribute the agents to the participants at study visit 1. The handling and distribution will be documented by the PI/co-investigator in locked and de-identified official study records. The participants will be asked to return containers at study visit 2 after completing the 5 day decolonization process at home. This will allow for drug reconciliation checks to document drug assigned, drug consumed and drug remaining. This reconciliation will be logged on the drug reconciliation form and signed and date by the study team. The returned containers will be collected by the study team and then returned to the NYULMC Investigational Research Pharmacy for final reconciliation and destruction on site.

7 Study Procedures and Schedule

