 - Assessment of study agent adherence will occur at each study visit based on questionnaires completed by the participants and assessment of study drug containers returned by participants to study team members after use.
- Decolonization: Subjects will all be instructed to performed the following decolonization protocol at home:
 - Apply the study drug topically to their nares and peri-rectal area twice daily (morning and night) for 5 consecutive days.
 - Perform environmental procedures to help eradicate MRSA from the home and prevent recolonization which includes washing all towels and linens with hot water and cleaning all frequently touched surfaces with bleach.
- Administration of questionnaires will occur at each study visit to assess change in medical history, change in infectious history, use of antibiotics, adherence to study drug agents and assessments of side effects
- A discussion of results of any study specific procedures will be provided to participant at the end of the study period after blinding has been lifted.

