7.3.2 Enrollment/Baseline

Enrollment/Baseline Visit (Visit 1, Day 0)

- Verify inclusion/exclusion criteria.
- Obtain demographic information, medical history, medication history, infection history from initial study questionnaire.
- Perform physical examination
- Subject randomization
- Provide study drug at this visit for home use.
- Instructions provided to the participants: The subjects will apply study drug topically inside the anterior nares and peri-rectal area twice a day (morning and night) for five consecutive days. They will also follow the environmental procedures in the attached instructions to help eradicate MRSA from the home.

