8.4.2 Serious Adverse Event Reporting

Serious Adverse Events will be reported in written format by the PI/co-investigator to the IRB and the industry partner within 7 days. The PI will be responsible for completing and signing off on the SAE reports.

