10.4.5 Adherence and Retention Analyses

Adherence to the protocol will be collected and documented using the data collection form (in appendix uploaded into study-related documents). Subjects will be asked to report the use of the provided ointment in follow-up questionnaire which will be administered at the follow-up study visit conducted one week after completion of study decolonization protocol. The subjects will receive phone calls from study team members as reminders to use the study drug provided. Additionally, containers from the drug provided will be collected at the same follow-up study visit to assess use. Subject retention/follow up will be assessed via phone call when subject fails to return for study visit within three weeks of completion of decolonization protocol. Additional comments due to loss to follow-up will be recorded after scheduled phone call. Discontinuation of intervention will occur if serious side effect (anaphylaxis) occurs.

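### Section 10.4.4 takes adverse events from a form completed before hospital discharge, which covers none of the home dosing days and contradicts the visit schedule and Section 8.3

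*Combined protocol and SAP*

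**What the plan says.** Section 10.4.4 names one source for the safety analysis: "Patients will be monitored for the occurrence of possible adverse events using a standardized data collection form prior to hospital discharge". It gives no analysis population, no observation window and no summary by arm.

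The sections on drug supply and use place exposure elsewhere. The Visit 1 procedures say "Provide study drug at this visit for home use". Section 7.1.1 says "Subjects will all be instructed to performed the following decolonization protocol at home", and Section 6.2 says "The participants will be asked to return containers at study visit 2 after completing the 5 day decolonization process at home". The length of exposure is set in Section 6.1.9: "Each ointment will be applied for five consecutive days". Under Section 5.1, a visit to the study team at the ODA clinic is an alternative to admission.

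Other sections collect adverse events differently:

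- Sections 7.3.3 and 7.3.4 record them from a questionnaire at Visits 2 and 3. The Schedule of Events marks the adverse event check at those two visits only.
- Section 8.3 has the investigator ask at each visit about events since the previous one. Recording runs from consent to 7 days (non-serious) or 30 days (serious) after the end of participation.
- Section 2.4.1 adds a telephone check-in with the parent and tells families to call if a side effect occurs.
- Sections 5.7.2 and 7.3.5 add a telephone call and a final questionnaire for children who withdraw.

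Section 10.4.4 refers to none of these.

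**The concern.** A form closed at discharge belongs to a trial in which treatment is given during the admission. Here the course starts after the drug is handed over for home use. Read literally, 10.4.4 would have the analyst tabulate a period before exposure for inpatient recruits, and would supply no form for a child who was never an inpatient.

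Tolerability is part of what this trial can add. Section 2.4.1 says use on mucosal surfaces has not been widely evaluated, and Section 5.3 says there are no current paediatric studies for this indication. Adverse events related to the drug are an exploratory endpoint in Section 4.2.3, yet Section 10.4.11 plans no exploratory analyses. That leaves 10.4.4 as the only place where their analysis could be specified. If its stated source were used, the adverse event table would describe the wrong period, and few events in it would say little about the ointment.

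**Working it through.** There is no stated figure to reproduce. The check compares the sections and works out the timeline from the visit windows.

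**Step 1. Does the 10.4.4 source overlap exposure?** The drug is dispensed at Visit 1, Day 0 (7.3.2), and used at home for 5 days (6.1.9, 6.2, 7.1.1). A form completed before discharge ends before home use begins, so it covers 0 of 5 home dosing days for an inpatient recruit. A clinic recruit need not have been admitted (5.1), so there need be no discharge and no form.

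**Step 2. When do the other sections first ask about events after dosing?**

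- Visit 2 is Day 14 ± 5: 14 − 5 = Day 9 to 14 + 5 = Day 19.
- Visit 3 is Day 35 ± 15: 35 − 15 = Day 20 to 35 + 15 = Day 50.

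Both fall after the course. Because 8.3 asks about the time since the last visit, the Visit 2 inquiry reaches back over all the dosing days.

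**Step 3. How long after the last application is the first examination after dosing?** The start day is not fixed, so assume Day 0 or Day 1. Five consecutive days then end on Day 4 or Day 5.

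- Shortest gap: Day 9 − Day 5 = 4 days.
- Longest gap: Day 19 − Day 4 = 15 days.

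Section 5.7.2 says "Adverse events from the drug are local at the site of application and should subside with the discontinuation of the product". On the protocol's own account, a local reaction may have gone by the time the nares and peri-rectal area are examined. What remains is what the parent or child remembers.

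**Step 4. Is there scheduled contact during the dosing days?** No visit falls within them. The telephone check-in in 2.4.1 has no stated timing and is in neither 7.3 nor the Schedule of Events. Section 10.4.5 mentions calls, but for another purpose: "The subjects will receive phone calls from study team members as reminders to use the study drug provided". Their purpose implies that they fall within the dosing days, but the section gives no number or dates.

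**Step 5. Notification times.** Section 10.4.4 has the study team and the IRB notified within one day of serious events that may be adverse reactions. Section 8.4.2 says "Serious Adverse Events will be reported in written format by the PI/co-investigator to the IRB and the industry partner within 7 days", and Section 8.4.1 also gives 7 days for serious events. The scope and form differ, and both can be met by a prompt notice followed by a written report. The text does not say that this is intended.

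**The case against.** The strongest reply is that 10.4.4 contains one misplaced sentence and the rest of the protocol collects the data properly. Much of this stands. Section 8.3 asks about events since the last visit and records onset, severity, relationship and resolution, so Visit 2 covers every dosing day by recall. Itch and stinging are symptoms that a questionnaire can pick up after they resolve. Section 10.3 lists side effects as a database variable alongside the blinded arm, so the data for a table by arm are planned. Withdrawn children are contacted (5.7.2, 7.3.5), and a medical monitor reviews adverse effects at least semiannually (8.7).

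A reader might infer from 10.4.4 that the trial collects no events from the exposure period, or that its safety data could not reveal poor tolerability. The documents do not support either reading, because the routes above are operational and cover the dosing days. Nor are the one-day and 7-day times a clear contradiction.

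The reply does not rescue the sentence itself. Section 10.4.4 is where the analysis is defined, and the source it names is incompatible with home dosing and with clinic recruitment. Section 10.1 promises a separate full SAP, but it also says that key elements are set out in this document, and this element is wrong.

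**Conclusion.** The point holds as an internal inconsistency in the safety analysis, not as a failure to collect safety data. The source named in 10.4.4 covers 0 of the 5 home dosing days, is not assured for clinic recruits, and conflicts with 7.3.3, 7.3.4, 8.3 and the Schedule of Events. The section also leaves the population and the summary by arm unstated.

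A secondary weakness is that local reactions rest mainly on recall, since the first examination after dosing comes about 4 to 15 days after the last application. That range assumes dosing starts on Day 0 or 1 and runs the full five days. Asking during dosing would be an improvement; relying on recall is not an error. The efficacy analysis is unaffected.

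**What to change.** **Correct the rule.** Replace the first sentence of 10.4.4 with text to this effect: the safety analysis uses adverse events recorded over the window in Section 8.3, from Visits 2 and 3, telephone contacts, and the withdrawal or early-termination questionnaire and call (5.7.2, 7.3.5). Events after first application are tabulated by arm for all children who applied any ointment. Keeping the 8.3 window avoids a new conflict. Naming the withdrawal contacts keeps in children who stop because of irritation.

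**Cheap addition.** In the reminder or check-in calls, ask a fixed question on local irritation by site (itch, redness, stinging). Time at least one call within the dosing days and list the calls in the Schedule of Events.

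**Clarify.** State how the one-day IRB notification in 10.4.4 relates to the 7-day written report in 8.4.1 and 8.4.2.

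The cost is a reworded paragraph, a row in the Schedule of Events and slightly longer calls. No visits are added.

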10.4.5 Adherence and Retention Analyses

Adherence to the protocol will be collected and documented using the data collection form (in appendix uploaded into study-related documents). Subjects will be asked to report the use of the provided ointment in follow-up questionnaire which will be administered at the follow-up study visit conducted one week after completion of study decolonization protocol. The subjects will receive phone calls from study team members as reminders to use the study drug provided. Additionally, containers from the drug provided will be collected at the same follow-up study visit to assess use. Subject retention/follow up will be assessed via phone call when subject fails to return for study visit within three weeks of completion of decolonization protocol. Additional comments due to loss to follow-up will be recorded after scheduled phone call. Discontinuation of intervention will occur if serious side effect (anaphylaxis) occurs.

10.4.6 Baseline Descriptive Statistics

We will assess differences in baseline descriptive statistics between the intervention groups. These variables include age, sex, history of MRSA infections, history of chronic skin conditions, and recent antibiotic use.

10.4.7 Planned Interim Analysis

Not applicable

10.4.7.1 Safety Review

Study enrollment and administration of study drug will be halted if serious adverse events are noted across multiple participants. If it was deemed that enrollment and administration of drug needed to be stopped, it would pertain to the entire study including participants in both arms.

10.4.7.2 Efficacy Review

Study enrollment and administration of study drug will be halted if serious adverse events are noted across multiple participants. If it was deemed that enrollment and administration of drug needed to be stopped, it would pertain to the entire study including participants in both arms. Interim analysis is not planned for efficacy review.

CONFIDENTIAL

This material is the property of the NYU School of Medicine and Langone Medical Center. Do not disclose or use except as authorized in writing by the study sponsor
Interventional Template Version: 28 APR 2017

10.4.8 Additional Sub-Group Analyses

We will assess differences in baseline descriptive statistics between the intervention groups. These variables include age, gender, history of MRSA infections, history of chronic skin conditions, and recent antibiotic use.

10.4.9 Multiple Comparison/Multiplicity

Not applicable

10.4.10 Tabulation of Individual Response Data

De-identified patient data will be listed measure (blinded) and pre-defined study follow up time points as illustrated in the Schematic of Study design on page 2 of this document.

10.4.11 Exploratory Analyses

None planned

10.5 Sample Size

The table below presents ranges of the required sample size based on the primary trial endpoint of the change in nasal/rectal colonization of MRSA from baseline to 1 week after completion of decolonization protocol at approximately 80% power. It provides a range of sample size depending on the potential effectiveness of retapamulin.

Computed N Per Group		
Proportion Diff	Actual Power	N Per Group
0.30	0.809	42
0.35	0.801	32
0.40	0.807	26
0.45	0.822	22
0.50	0.811	18
0.55	0.802	15
0.60	0.808	13
0.65	0.841	12

The sample size calculation was based on prior literature indicating a 60% decolonization rate; a 45% difference in decolonization between groups (60% retapamulin vs 15% placebo/spontaneous decolonization) at 80% power. This is taken into account a 15% spontaneous decolonization rate as reported in the literature. Power calculation analyses were performed in SAS 9.3 (SAS Institute, Cary NC) using fisher's exact conditional test for two proportions (Walters normal approximation with exact conditional distribution). A 20% lost to follow up was estimated and added to the final sample size number. Therefore, the total number of participants enrolled will be 54 subjects – 27 in each of the two arms of the study.

It is estimated that 0.8-6% of the general population is colonized with MRSA. Colonization in persons with previous infection is estimated to be 20%. We suspect this percent is higher in the particular population we aim to study as it is a high risk population for MRSA colonization and infection. Therefore we estimate screening 500 participants to meet the sample size goal of our study.

CONFIDENTIAL

This material is the property of the NYU School of Medicine and Langone Medical Center. Do not disclose or use except as authorized in writing by the study sponsor

We will use fisher exact test at alpha .05 to determine a significant difference between treatment groups (retapamulin vs placebo). Participants who withdraw before the 1 week primary endpoint will be excluded from analysis as the primary end point will not be recorded.

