This material is the property of the NYU School of Medicine and Langone Medical Center. Do not disclose or use except as authorized in writing by the study sponsor
Interventional Template Version: 28 APR 2017

Interestingly, no difference in methicillin-susceptible *S. aureus* (MSSA) colonization prevalence was observed between children from high-risk and low-risk communities. However, children from these high-risk areas were 2.8 times as likely to be colonized with MRSA (prevalence 9% vs 3% [p=0.04]). Likewise, the MRSA infection rate per 1,000 patient days was 36 for children from high-risk areas versus 3.9 in children from low-risk areas (p<0.0001). All isolates from patients in high-risk zip codes analyzed to date belong to genotype USA300, the predominant CA-MRSA clone in the US. This data suggests there is a geographically defined outbreak of CA-MRSA in children and these isolates form a distinct clade within the common USA300 MRSA lineage.

Moreover, the majority of the clinical strains from the outbreak cluster carry the plasmid encoding the *mupA* gene, which confers the mupirocin-resistant (Mup-R) phenotype. Phenotypic analysis confirmed mupirocin resistance in 84% (39/55) of the outbreak subclone isolates compared to none (0/17) in the USA300 CA-MRSA control isolates. This finding has significant clinical impact, as there are no validated approaches to decolonize these children and families, and many such patients are re-hospitalized with recurrent infections. In addition, CA-MRSA transmission in the community is ongoing and transmissions have been observed at our institution. Without an adequate way to decolonize Mup-R MRSA-positive patients, we risk expansion of the outbreak strain to lower risk patients and to communities outside the high risk geographic area.

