5.1 Inclusion Criteria

In order to be eligible to participate in this study, an individual must meet all of the following criteria:

1. Admission to the general pediatric floor and pediatric intensive care units at NYU Langone Medical Center or visit to study team members at ODA clinic (Park Ave locations) in Williamsburg Brooklyn.
2. Ages 9 months to 17 years
3. Residing in the zip codes which reflect Orthodox Jewish neighborhoods where there is a current outbreak of this strain of MRSA.
4. Nasal and/or rectal culture positive for mupirocin-resistant methicillin-resistant *Staphylococcus aureus* (MRSA)

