After informed consent, and assent when appropriate is obtained, screening nasal and peri-rectal cultures will be performed on these participants to determine if they are eligible to enroll. Eligibility includes either nasal or rectal positive for MRSA. Informed consent will take place either at NYULMC on the inpatient ward while they are admitted, at ODA clinic during time of screening, or at Fink Children's Ambulatory Center when present for a routine follow up visit. Participants will be asked to fill out a study questionnaire which asks about medical history, medication use, history of MRSA infections and prior use of antibiotics and specific MRSA medications. The study team will ask participants for this information via questionnaire only; it will not be gathered from their medical records. They study team will not access medical records or charts for participants.

The participants will be required to follow up at pre-defined time points throughout the 6 weeks study period to obtain follow up swabs, complete questionnaires regarding interim change in medical history or side effects experienced, and to collect containers from study drugs. Retention will be enhanced through telephone reminders of study visit appointments as well as payments for participation in the study. In addition, follow up for study visits for the participants recruited at NYULMC will occur at NYU Pediatric Infectious Diseases outpatient clinic as per routine medical management, at NYU Langone Main Campus, Greenberg Hall, or at ODA clinic (Park Ave location) in Brooklyn.

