5.6 Total Number of Participants and Sites

The total number of participants enrolled will be 54 subjects. 27 in each of the two arms of the study.

Recruitment will end when approximately 54 participants are enrolled and have completed the study protocol. It is expected that approximately 54 participants will be enrolled in order to produce 44 evaluable participants as we estimate a 20% drop out rate. The participants will be recruited at NYULMC Tisch Hospital or ODA clinic in Brooklyn.

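### Does the estimate of 500 children to be screened need changing because the protocol's own 9% MRSA prevalence would yield fewer than 54 participants?

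*Combined protocol and SAP*

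**What the plan says.** Section 10.5 sets the target: "the total number of participants enrolled will be 54 subjects – 27 in each of the two arms of the study". It then cites MRSA colonization of 0.8-6% in the general population and 20% after previous infection, expects a higher rate in the study community without giving a number, and concludes: "Therefore we estimate screening 500 participants to meet the sample size goal of our study". It states no yield and no resistance fraction.

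Section 2.1 reports that children from the high-risk zip codes were "2.8 times as likely to be colonized with MRSA (prevalence 9% vs 3% [p=0.04", and gives "mupirocin resistance in 84% (39/55) of the outbreak subclone isolates".

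Inclusion criterion 4 (section 5.1) reads "Nasal and/or rectal culture positive for mupirocin-resistant methicillin-resistant", followed by the organism's name. Section 5.4 is looser: "Eligibility includes either nasal or rectal positive for MRSA".

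Section 5.6 says when recruitment stops: "Recruitment will end when approximately 54 participants are enrolled and have completed the study protocol". It links enrolment to the evaluable number: "approximately 54 participants will be enrolled in order to produce 44 evaluable participants as we estimate a 20% drop out rate".

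**The concern.** Section 10.5 draws its 500 from general rates and passes over the prevalence that the protocol itself reports for the target community. At that prevalence 500 screens fall short of 54 even under the looser wording of section 5.4, and further short once mupirocin resistance is required. The resistance figure also disagrees with itself, since 39 of 55 is not 84%.

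If the shortfall is real, several hundred more children than stated would have to be consented and swabbed within the two-year study. If the team treated 500 as a limit, the trial would end with too few evaluable children for its stated 80% power.

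**Working it through.** **The plan's own figures.** The sample size reproduces. For 60% versus 15% with 22 per arm, the Walters approximation (two-sided alpha 0.05) gives power 0.8216 against the tabulated 0.822, and all eight rows of the table match. Then 22 x 1.2 = 26.4, rounded up to 27 per arm, or 54 in total. The 500 does not reproduce, because section 10.5 gives no inputs for it.

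**Inputs.**
- Target: 54 (10.5)
- Stated screens: 500 (10.5)
- Prevalence in high-risk zip codes: 9% (2.1)
- Resistant share: 84% as printed, or 39/55 = 70.9% (2.1). For comparison, 0.84 x 55 = 46.2, so 84% would correspond to about 46 of 55.
- Other cited prevalences: 6% (upper general-population figure) and 20% (previous infection) (10.5)

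**Formulas.** Expected eligible = 500 x prevalence x resistant share. Screens needed = 54 / (prevalence x resistant share). Exclusions and refusals are ignored.

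| Prevalence | Resistant share | Eligible per 500 | Screens for 54 |
|---|---|---|---|
| 6% | 70.9% | 21.3 | 1,270 |
| 6% | 84% | 25.2 | 1,072 |
| 9% | not required | 45.0 | 600 |
| 9% | 70.9% | 31.9 | 847 |
| 9% | 84% | 37.8 | 715 |
| 20% | 70.9% | 70.9 | 381 |
| 20% | 84% | 84.0 | 322 |

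**Prevalence at which 500 works.** 0.108 / 0.84 = 12.9% and 0.108 / 0.709 = 15.2%. Both lie between the 6% and 20% cited in section 10.5.

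**Chance of success if 9% were exact.** The binomial probability that 500 screens yield at least 54 is 9.4% on MRSA alone, 0.6% with an 84% resistant share and 0.01% with 70.9%.

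**How firm is the 9%?** Section 2.1 gives no denominator. As an assumption, take 130 children per group: 12/130 versus 4/130 gives p = 0.039, close to the reported 0.04, although the ratio is 3.0 rather than 2.8. The 95% Wilson interval for 12/130 is 5.4% to 15.4%. The screens needed then run from 54 / (0.154 x 0.84) = 417 to 54 / (0.054 x 0.709) = 1,410. The stated 500 lies inside that range.

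**Does anything depend on 500?** Section 5.6 ends recruitment on the number enrolled, and no section sets a maximum number screened. Each child's screening isolate is tested for mupirocin resistance (section 7.1.1), so the share in section 2.1 decides nobody's eligibility and enters no analysis.

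**The case for a change.** The best case for a change is that the protocol holds a directly relevant prevalence, does not use it, and states a number that this prevalence makes unlikely. The 20% does not rescue it, because it describes people with a previous infection, while section 4.1 recruits inpatients by zip code whatever the reason for admission. The resistant share may also be generous: it comes from outbreak-subclone isolates, and the USA300 control isolates were 0/17 resistant. Exclusions and refusals lower the yield further. Correcting one estimate and one percentage would cost almost nothing.

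Most of this stands as a remark on documentation. It does not show that 500 is wrong. Section 2.1 does not say which body sites lie behind the 9%. This trial swabs nose and peri-rectal area and counts either, and it adds a clinic route fed by referral; both could raise the yield, though the documents quantify neither. Replacing 500 with 715 to 847 would multiply a prevalence of unknown precision by a resistance share from selected isolates, which is no firmer.

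A power argument can also be made. If screening stopped at 500, 32 to 38 enrolled with 20% loss would leave about 13 to 15 evaluable per arm (32 x 0.8 / 2 = 12.8; 38 x 0.8 / 2 = 15.2), where exact Fisher power is 0.58 to 0.59 against 0.827 at 22 per arm. The plan contains no such stop, so this does not describe the trial as designed.

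**Conclusion.** The arithmetic behind the concern is right: at 9% prevalence, 500 screens give about 45 carriers, or about 32 to 38 with mupirocin resistance, against a target of 54. It rests on two assumptions, that the 9% applies to nasal and/or rectal carriage in the children actually screened, and that the outbreak-isolate resistance share applies to colonizing strains. The documents establish neither, so 500 is unsupported rather than shown to be wrong.

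No change to the plan is needed. The 500 is a workload forecast. Enrolment of about 54, the 22 evaluable per arm, the Fisher test and the 80% power are the same whether 500 or 850 children are screened. Section 4.1 gives bed numbers, but no admission or screening rate appears anywhere, so whether a larger number fits into two years cannot be judged. The team will see its true yield as screening proceeds and can continue to 54.

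The 84% beside 39/55 is a clerical slip in the background, and the looser eligibility sentence in section 5.4 reads as shorthand for criterion 4, which every participant must meet.
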